8.1. Primary Efficacy Endpoint

The primary endpoint of this study is the proportion of subjects in sustained remission at Week 52, defined as having achieved all of the following criteria:

1. Remission at Week 12

Remission is defined as having achieved the 2 following criteria:

- a. Clinical remission is defined as absence of clinical signs and symptoms of GCA
And
- b. Normalization of ESR (<30mm/hr) and CRP (<1mg/dL).

A subject in clinical remission is a subject that does not have any signs and symptoms, which is also determined by a lack of flare for the subject. If a subject does have a flare, they will have one or more signs and symptoms, and therefore are not considered as being in clinical remission. A subject without any flare at the Week 12 visit will be considered in clinical remission.

The following rule will be used to assess remission at Week 12:

“Has the patient flared since their last visit?” should be answered “No” at Week 12 visit on the Clinical Assessment of GCA eCRF page and ESR laboratory results value at Week 12 should be < 30mm/hr and CRP laboratory results value at Week 12 should be < 1mg/dL.

AND

2. Absence of disease flare following remission at Week 12 through Week 52

Flare is determined by the investigator and defined as the recurrence of symptoms attributable to active GCA, with or without elevations in ESR and/or CRP.

The following rule will be used to assess absence of disease flare following remission at Week 12 through Week 52:

“Has the patient flared since their last visit?” should be answered “No” at each scheduled and unscheduled visit from any visit after Week 12 up to Week 52 on the Clinical Assessment of GCA eCRF page.

AND

3. Completion of the assigned prednisone taper protocol (to Week 52)

“Can the patient continue with the protocol defined taper” on the Clinical Assessment of GCA eCRF page should be answered “Yes” at all scheduled and unscheduled visits between Baseline and Week 48.

AND

4. No requirement for rescue therapy at any time through Week 52

If any concomitant corticosteroid medication when the unit is not in (Actuation, Application, Area under curve, Cubic centimeter, Cells, Cells per kilogram, Fingertip unit, Drops, Gum, Inhalation, Kilocalories, Minimum alveolar concentration, Mega becquerels (MBq), Millicurie, Nebule, Patch, Powder, Puff, Ring, Spray, Suppository) or any of concomitant non-corticosteroid medication identified as “GCA related” with the question “Was drug administered as a rescue medication?” is ticked as “Yes” and if the first SC IP Date ≤ Concomitant medication start date ≤ Week 52 visit date, then subject will fail the criterion.

If all of the 4 criteria are met, subject will be considered in sustained remission at Week 52. If 1 of the 4 criteria is not met, the subject will be considered as not in sustained remission at Week 52.

For more details on imputation of missing data for the primary endpoint, please refer to [Section 4.6.2.1](#).

Given study termination, only the subset of subjects who attended the Week 52 visit or who discontinued study treatment or withdrew from study prior to the 10th of October 2017 will be included in this analysis.

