## **9.4. Key Elements of Analysis Plan**

### **9.4.1. Primary Efficacy Analyses**

The primary endpoint is a proportion of subjects in sustained remission at Week 52, defined as having:

5. Achieved remission (absence of clinical signs and symptoms of GCA and normalization of ESR [ $<30$  mm/hr] and CRP [ $<1$  mg/dL]), by Week 12
6. Absence of disease flare (recurrence of symptoms attributable to active GCA, with or without elevations in ESR and/or CRP) following remission at Week 12 through Week 52
7. Completed the assigned prednisone taper protocol
8. No requirement for rescue therapy at any time through Week 52.

Subjects who do not achieve remission within 12 weeks, require rescue therapy, discontinue treatment during the study or withdraw early from the study for any reason or do not follow the assigned prednisone taper will be recorded as non-responders in the analysis of the primary endpoint.

The proportion of subjects with sustained remission at week 52 in the sirukumab 100 mg SC q2w plus 6 month prednisone (Arm A) versus placebo plus 6 month prednisone (Arm D) will be analysed using a logistic regression model controlling for the stratification factor of baseline prednisone dose. The model will also include the treatment arms. Odds ratios and 95% confidence intervals will be produced.

If however a non-parametric approach is more appropriate then the Cochran-Mantel-Haenszel will be used.

As a supportive of the primary endpoint, the percentage of subjects meeting each of the components of the primary endpoint at Week 52 will be presented and the treatment effect on those components will be evaluated.

Further details of the analysis are included in the RAP.

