3.2.1. Study Endpoints for Part A

3.2.1.1. Primary Efficacy Endpoint

The primary endpoint of this study is the proportion of subjects in sustained remission at Week 52, defined as having achieved all of the following:

1. Remission at Week 12, where remission is defined as:

- a. Clinical remission at Week 12, defined as absence of signs and symptoms of GCA and
 - b. Normalization of ESR [$<30\text{mm/hr}$] and CRP [$<1\text{mg/dL}$]
- AND**
2. Absence of disease flare following remission at Week 12 through Week 52, where disease flare defined as recurrence of symptoms attributable to active GCA, with or without elevations in ESR and/or CRP
- AND**
3. Completion of the assigned prednisone taper protocol
- AND**
4. No requirement for rescue therapy at any time through Week 52

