6.2.2. Disease Characteristics of GCA at Baseline

The following variables will be summarized:

- Baseline prednisone dose (stratification factor)
- Acute-phase proteins (Baseline CRP < 1mg/dL and ESR < 30mm/hr)
- Remission status: clinical remission at Baseline and normalization of CRP and ESR. A subject in clinical remission is a subject that does not have any signs and symptoms, which is also determined by a lack of flare. If a subject does have a flare, they will have one or more signs and symptoms, and therefore are not considered as being in clinical remission. A subject without any flare at the Baseline visit will be considered in clinical remission.
- Baseline Patient's Global Assessment of Disease Activity VAS
- Baseline signs and symptoms: cranial signs or symptoms, symptoms of PMR, other signs or symptoms attributable to GCA or PMR flares, and visual signs or symptoms.

All data will be listed in detail.

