8.2.1.1. Statistical Analysis

The cumulative prednisone dose will be summarized by treatment group and visit. Interquartile range (IQR) will also be displayed in summary statistics. The summary statistics will be generated for the total cumulative prednisone as well as for the study drug and the CS rescue therapy separately. Cumulative dose will be listed.

8.2.2. Proportion of Subjects in Sustained Remission over Time from Week 12 to Week 52

For each visit (referred to as Week X in the algorithm below) from Week 12 to Week 48, the definition of sustained remission is similar to Week 52:

1. Remission at Week 12

Remission is defined as having achieved the 2 following criteria:

- c. Clinical remission is defined as absence of clinical signs and symptoms of GCA
- And
- d. Normalization of ESR (<30mm/hr) and CRP (<1mg/dL).

A subject in clinical remission is a subject that does not have any signs and symptoms, which is also determined by a lack of flare for the subject. If a subject does have a flare, they will have one or more signs and symptoms, and therefore are not considered as being in clinical remission.

The following rule will be used to assess remission at Week 12:

“Has the patient flared since their last visit?” should be answered “No” at Week 12 visit on the Clinical Assessment of GCA eCRF page and ESR laboratory results value at Week 12 $< 30\text{mm/hr}$ and CRP laboratory results value at Week 12 $< 1\text{mg/dL}$.

AND

2. Absence of disease flare following remission at Week 12 through Week X

Flare is defined as recurrence of symptoms attributable to active GCA, with or without elevations in ESR and/or CRP.

The following rule will be used to assess absence of disease flare following remission at Week 12 through Week X:

“Has the patient flared since their last visit?” should be answered “No” at each scheduled and unscheduled visit from any visit after Week 12 up to Week X on the Clinical Assessment of GCA eCRF page.

AND

3. Completion of the assigned prednisone taper protocol (to Week X)

“Can the patient continue with the protocol defined taper” on the Clinical Assessment of GCA eCRF page should be answered “Yes” at all visits between Baseline and the visit before the Week X visit.

AND

4. No requirement for rescue therapy at any time through Week X

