8.2.3. Time to First Disease Flare after Clinical Remission

Only subjects who achieve clinical remission will be included in this analysis. To address this endpoint, the following definitions will be used:

Clinical remission: A similar approach as for the primary endpoint will be used: Clinical remission is defined as absence of clinical signs and symptoms of GCA

A subject in clinical remission is a subject that does not have any signs and symptoms, which is also determined by a lack of flare for the subject. If a subject does have a flare, they will have one or more signs and symptoms, and therefore are not considered as being in clinical remission.

The following rule will be used to assess Clinical remission:

“Has the patient flared since their last visit?” should be answered “No” at a given visit. Clinical remission can occur at any visit between Baseline and Week 52.

Time to first disease flare after clinical remission is the time (days) from the first clinical remission date to the earliest disease flare date:

Disease flare after clinical remission: Date of first disease flare (as collected in the assessment of GCA disease activity) after clinical remission as defined above.

Time to first disease flare (days) = Date of disease flare date – Date of clinical remission + 1 day

Subjects without disease flare at the time of analysis and who have completed the Week 52 visit will be censored at the date of the Week 52 visit. Subjects without disease flare at the time of analysis withdrew from the study or die will be censored at the date of early withdrawal or death. Data observed at or prior to the baseline visit will not be included in this analysis. Handling of missing data in the clinical remission component will be as described in [Section 4.6.2.1](#).

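### Week 12 clinical remission is derived from absence of flare alone, so unresolved GCA symptoms with normal ESR and CRP can count as remission

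*SAP*

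**What the plan says.** **Definition.** Protocol 9.4.1 makes the first component of the primary endpoint "Achieved remission (absence of clinical signs and symptoms of GCA and normalization of ESR" and CRP, by Week 12, and treats subjects who do not reach remission within 12 weeks as non-responders. SAP 3.2.1.1 has "Clinical remission at Week 12, defined as absence of signs and symptoms of GCA", with normal ESR and CRP. SAP 8.1 repeats this.

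**Derivation.** SAP 8.1 then gives the operative rule. The eCRF item asking whether the patient has flared since the last visit must be answered no at Week 12, ESR must be below 30 mm/hr and CRP below 1 mg/dL. The clinical part rests on the statement "A subject without any flare at the Week 12 visit will be considered in clinical remission". The reason given, in 8.1 and again in 8.2.2, is "If a subject does have a flare, they will have one or more signs and symptoms".

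**Flare.** In the same section, "Flare is determined by the investigator and defined as the recurrence of symptoms attributable to active GCA", with or without raised ESR or CRP.

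**Other uses.**
- SAP 6.2.2, Baseline remission status: "A subject without any flare at the Baseline visit will be considered in clinical remission".
- SAP 8.2.2, sustained remission over time: the same Week 12 rule.
- SAP 8.2.3, time to first flare: a no on the flare item is enough, with no laboratory condition. "Clinical remission can occur at any visit between Baseline and Week 52", and "Data observed at or prior to the baseline visit will not be included in this analysis".

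**The concern.** The SAP argues that a flare implies signs or symptoms, then applies the converse, that no flare implies none. The converse fails for symptoms that were present at entry and never went away, because these have not recurred.

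Week 12 remission is the gateway to the primary endpoint and to sustained remission at every later visit. In 8.2.3 the same proxy decides who enters the risk set and when the clock starts. At stake are the reported remission proportions, the Baseline remission status, and the time-to-flare risk set and origin.

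**Working it through.** The plan gives no figure for this rule, so the check compares the texts and then works out the effect per subject.

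**1. Does the rule contain a symptom check?** No. The Week 12 conditions in SAP 8.1 are the flare item, ESR and CRP. Criterion 2 repeats the flare item at visits after Week 12, criterion 3 uses the taper-continuation item, and criterion 4 uses rescue medication records. None tests for absence of signs and symptoms.

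**2. Can symptoms be present without a flare?** Yes, on the plan's own terms.
- Flare is a recurrence (SAP 8.1).
- Protocol 5.1 requires active GCA within 6 weeks of randomization and clinically stable disease at Baseline. It does not require subjects to be symptom-free.
- SAP 9.4 plans counts of each sign and symptom at each scheduled visit, separately for no flare and flare.
- The item covers an interval, not the state at the visit. A flare recorded at Week 8 with symptoms continuing at Week 12 could be answered no at Week 12.

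**3. Do ESR and CRP close the gap?** Not reliably. Protocol 7.9.1 says these markers do not consistently track disease activity. Protocol 2.2 says IL-6 drives acute-phase reactants, so the limits may be easier to meet under an anti-IL-6 antibody. The error could therefore differ by arm, but the documents do not establish a direction. In 8.2.3 no laboratory condition applies at all.

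**4. Is the change explained by termination?** No. The changes listed in SAP 1.1 do not include it.

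**5. Effect on a proportion.** One misclassified subject who also meets criteria 2 to 4 adds 100/n percentage points. Here n is the arm's number analysed under SAP 8.1: Week 52 attenders plus those who discontinued treatment or withdrew before 10 October 2017. The documents do not give n. Values below 34 are assumed; 34 and 51 are the planned arm sizes, taken as an upper limit because the study stopped early.

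| n | 100/n (points) |
|---|---|
| 5 (assumed) | 20.0 |
| 10 (assumed) | 10.0 |
| 20 (assumed) | 5.0 |
| 34 (planned, Arms C, D, E) | 2.9 |
| 51 (planned, Arms A, B) | 2.0 |

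**6. Effect on the time origin.** Post-baseline visits in the Part A schedule fall at Weeks 2, 4, 8 and 12. With Baseline data excluded, a subject with no flare gets an origin at Week 2, whatever the symptoms. If symptoms are first absent at a later visit, the origin is too early by (later week − 2) × 7 days:
- Week 4: (4 − 2) × 7 = 14 days
- Week 8: (8 − 2) × 7 = 42 days
- Week 12: (12 − 2) × 7 = 70 days

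A subject whose symptoms never resolve should not be in the risk set, yet enters it at Week 2.

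**The case against.** The strongest reply has five parts.

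**The consequence depends on how sites answer the item.** An investigator may record a flare when symptoms persist, and the eCRF instructions are not in the documents. This stands as a limit on size. Neither the item nor the flare definition requires that answer, however, so the rule as written allows the error.

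**The flare item is where symptoms are attributed to active GCA.** A rule based on any recorded sign could fail subjects for adrenal insufficiency, other illness or old damage. Protocol 6.3 asks investigators to separate inflammatory flare from non-inflammatory symptoms. This stands, and the fix must allow for attribution.

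**Much of the information is already planned.** SAP 9.4 tabulates signs and symptoms by flare status, SAP 8.1.1 lists the clinical assessments, and SAP 6.2.2 shows Baseline symptoms beside Baseline remission status. A reader could reclassify by hand. None of these outputs feeds the remission derivation or the 8.2.3 origin.

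**The affected group is narrow and the outputs are descriptive.** Such a subject must also have no later flare, continue the taper and need no rescue. Both points stand. They limit the harm but do not make the derivation match its definition.

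**The SAP postdates termination** (SAP 7.3 cites a source retrieved in January 2018), so changing a primary criterion needs justification. The change would bring the derivation back to the protocol's definition, and that reason can be stated.

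**Conclusion.** The concern holds. The SAP's derivation of clinical remission does not implement the definition in Protocol 9.4.1 and SAP 3.2.1.1 and 8.1, and no other section adds the missing symptom check. It can misclassify subjects on the first primary-endpoint criterion, on sustained remission over time and on Baseline remission status. It can also bring the time-to-flare origin forward.

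The number of subjects affected and the direction by arm are unknown. The per-subject effect ranges from 2.0 points at n=51 to 20 points at an assumed n=5, for subjects who also pass criteria 2 to 4. The 14, 42 and 70-day shifts apply to unflared subjects whose symptoms are first absent at Week 4, 8 or 12. No hypothesis test is affected, because SAP 8 limits efficacy to summary statistics. This should be fixed, but it does not undermine the study.

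**What to change.** Derive clinical remission at a visit as both:
- a no on the flare item; and
- no cranial, visual, PMR or other sign or symptom attributable to active GCA recorded on that visit's Clinical Assessment of GCA.

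Do not count fixed damage from earlier disease. The sign list in Protocol 7.3 includes permanent vision loss and stroke, which would otherwise bar remission indefinitely. At Week 12, combine this with ESR below 30 mm/hr and CRP below 1 mg/dL. Apply the same rule in SAP 6.2.2, 8.1, 8.2.2 and 8.2.3.

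If the eCRF does not capture attribution, keep the current rule and add two summaries by arm: the number of Week 12 remitters with any recorded sign or symptom, and the sustained remission proportion with those subjects counted as non-remitters.

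The cost is SAP wording and some derivation programming. The signs and symptoms are already collected, listed under 8.1.1 and tabulated under 9.4. The SAP should record that the reason is agreement with the protocol definition. Reported remission proportions may be lower.

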3.2.1.2. Secondary Efficacy Endpoints

- Cumulative prednisone dose over time
 - Proportion of subjects in sustained remission at each time point of assessment from Week 12 to Week 52, where sustained remission is defined as having achieved all of the following at each visit:
 1. Remission at Week 12:
 - a. Clinical remission at Week 12, defined as absence of signs and symptoms of GCA
And
 - b. Normalization of ESR [$<30\text{mm/hr}$] and CRP [$<1\text{mg/dL}$]
- AND**
2. Absence of disease flare following remission at Week 12 through Week X, disease flare defined as recurrence of symptoms attributable to active GCA, with or without elevations in ESR and/or CRP
- AND**
3. Adherence to the assigned prednisone taper protocol through Week X,
- AND**
4. No requirement for rescue therapy at any time through Week X
- Time to first disease flare after clinical remission
 - Number of disease flares per subject over time
 - Proportion of subjects requiring hospitalizations for disease flare and number of hospitalizations for disease flare over time
 - Patient-reported outcomes (PRO) including 36-item Short Form health survey version 2 (SF-36 v2) acute, EuroQol – 5 dimensions, 5 levels (EQ-5D-5L), Functional Assessment of Chronic Illness Therapy-fatigue (FACIT-Fatigue), Pain Numeric Rating Scale (NRS), Steroid Impact Questionnaire, Health Assessment Questionnaire – Disability Index (HAQ-DI), Patient Global Impression of Change (PGIC), Patient Global Assessment of disease activity (PtGA)

- Clinician-reported outcomes: Physician Global Assessment of disease activity (PhGA)
- Change from Baseline in ESR over time
- Change from Baseline in serum CRP over time

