4.6. Handling of Missing Data

4.6.1. Treatment Failure Definition

For the primary endpoint derivation, a treatment failure is defined as any subject who:

1. Discontinued permanently SC IP prior to completing week 52 visit due to any reason and continued in the study (i.e. follow-up off treatment)
- or
2. Withdrew from the study for any reason earlier than 10th October 2017, the study termination date.

A subject will be considered a treatment failure from the earliest date that the subject meets any of the 2 treatment failure criteria. Only withdrawals prior to 10th October 2017 will be considered, withdrawals on or after this date will likely be result of study termination at sponsor's request and not provide an accurate summary of treatment response.

A subject that temporarily has their treatment of SC IP put on hold, will not be considered as permanent discontinuations.

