The reasons for study withdrawal will also be summarized within this table for each Part of the study. The reasons for study withdrawal will be presented in the order they are displayed in the eCRF.

The following information will be summarized on the Safety Set on a separate table:

- Subjects who completed SC IP treatment:
 - Prednisone study drug treatment completed
 - Permanently discontinued prednisone study drug treatment prior to completing week 52 visit
- Subjects who permanently discontinued SC IP treatment prior to completing week 52 visit (this will include subjects who discontinue SC IP due to study termination)
 - Prednisone study drug treatment discontinued prior to completing week 52 visit
 - Completed prednisone study drug treatment

Treatment status and reason for discontinuation will be provided for SC IP (sirukumab or placebo) and prednisone study drug separately. Reasons for study treatment discontinuation will be presented in the order they are displayed in the eCRF. Listings of discontinuation of IP SC and prednisone study drug will be generated. The listings will include last dose date, and reasons for study treatment discontinuation.

A listing of reasons for study withdrawal will be generated. A listing of subjects continuing into Part B of the study will be produced.

Listings of planned and actual treatments for subjects, and of all subjects for whom the treatment blind was broken will be generated.

Subjects will be assigned to the actual treatment groups if they received:

Subcutaneous IP for more than 50% of their injections	Prednisone study drug for more than 50% of the doses	Actual treatment
S100	3m	B
	6m	A
	12m	A
	random	A
S50	3m	C
	6m	C
	12m	C
	random	C
Placebo	3m	D
	6m	D
	12m	E
	random	E

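### Permanently stopping prednisone study drug is not a failure in the sustained-remission derivation, so a subject who abandons the taper can still be scored a responder

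*SAP*

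**What the plan says.** Protocol 9.4.1 makes completion of the assigned taper one of four parts of the primary endpoint. It then states that subjects who, among other things, discontinue treatment or "do not follow the assigned prednisone taper will be recorded as non-responders". Protocol 6.1 uses the term study treatment for any combination of the products given, prednisone included.

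SAP 8.1 titles the third component "Completion of the assigned prednisone taper protocol (to Week 52" and derives it from a single item on the Clinical Assessment of GCA page, "Can the patient continue with the protocol defined taper". The answer must be Yes "at all scheduled and unscheduled visits between Baseline and Week 48". For the over-time endpoint, SAP 8.2.2 requires Yes "at all visits between Baseline and the visit before the Week X visit", while SAP 3.2.1.2 words the component as "Adherence to the assigned prednisone taper protocol through Week X".

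SAP 4.6.1 has two routes to treatment failure. One is "Discontinued permanently SC IP prior to completing week 52 visit due to any reason and continued in the study"; the other is study withdrawal before 10 October 2017. The extra condition at the end of SAP 8.2.2 again concerns the subcutaneous product only. SAP 5.1 nevertheless has a category, among subjects who completed the injections, for "Permanently discontinued prednisone study drug treatment prior to completing week 52 visit", and reports the reasons.

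**The concern.** The eCRF item looks ahead: it records whether the investigator thinks the patient can go on with the taper. It does not record whether doses were taken or whether the patient has stopped. None of the three places where a permanent stop could be caught (the taper component, the treatment-failure rule, the extra condition in SAP 8.2.2) looks at prednisone study drug status, although that status is collected.

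The proportion in sustained remission can therefore include subjects whom the protocol counts as non-responders. In a trial about remission while steroids are tapered on a fixed schedule, this component is part of what the endpoint means. SAP 1.1 lists the endpoint wording changed because of termination, and the taper component is not among those changes.

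**Working it through.** The plan attaches no figure to this rule, so the check is a trace through the derivation plus a count of schedule weeks.

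**1. One record through the SAP rules.** Take a subject in Arm A, C, D or E who receives every injection and attends Week 52. ESR and CRP are normal at Week 12. The subject permanently stops the blinded capsules at Week 16, the investigator keeps answering Yes, no flare is recorded and no steroid is ticked as rescue.

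| Rule | What the SAP reads | Result |
|---|---|---|
| Remission at Week 12 | flare item, ESR, CRP | met |
| No flare after Week 12 | flare item to Week 52 | met |
| Taper completion | can-continue item to Week 48 | met |
| No rescue | rescue box, start date up to Week 52 | met |
| Treatment failure (4.6.1) | SC product stopped, or study withdrawal | not triggered |

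The SAP scores sustained remission. Protocol 9.4.1 scores a non-responder.

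**2. Was this subject still on active taper at Week 16?** Inputs from SAP Table 3: open-label weeks o = 1 (20 mg start) to 7 (60 mg start); non-zero blinded weeks b = 5, 19 and 45 for the 3-, 6- and 12-month tapers. Active taper ends at Week o + b:

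- 3-month (Arm B): 1 + 5 = 6 to 7 + 5 = 12
- 6-month (Arms A, C, D): 1 + 19 = 20 to 7 + 19 = 26
- 12-month (Arm E): 1 + 45 = 46 to 7 + 45 = 52

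So yes in Arms A, C, D and E. In Arm B active doses are over by Week 12, and the conflict with the protocol there depends on treating the remaining zero-dose capsules as part of the assigned taper.

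**3. What the Week 48 cut-off can miss.** Active weeks after Week 48 are o + 45 − 48, and only in Arm E. Starts of 35, 40, 50 and 60 mg (o = 4, 5, 6, 7) give 1, 2, 3 and 4 weeks. In Arms A and D the last active dose falls by Week 26, so the cut-off misses none. The blinded capsules themselves follow one 45-week schedule, with the same number per day in every arm (SAP 4.2 and 7.2.2.2).

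**4. Size.** One misclassified subject moves an arm's proportion by 100/n points. At the planned sizes this is 100/51 = 1.96 or 100/34 = 2.94. These are reference values only. SAP 8.1 restricts the summary to subjects who attended Week 52, or who discontinued study treatment or withdrew before 10 October 2017, and the documents do not give that n. If n is half of plan, the points double.

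**5. Direction (assumption, for illustration).** Let a share m of true non-responders be scored as responders, starting from the planning rates of 30% (D) and 70% (A). With equal m in both arms the rates become 30 + 70m and 70 + 30m, and the difference is 40(1 − m): 38.0 points at m = 5% and 36.0 at m = 10%. With m = 10% in D only it is 70 − 37 = 33 points; in A only, 73 − 30 = 43. The documents give no m.

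**The case against.** The strongest reply has four parts.

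- *The timing is deliberate.* Because the item looks ahead, the Week 48 answer covers Weeks 48 to 52, and the answer at the visit before Week X covers the interval up to X. This largely stands. A reader might infer that every Week X result is wrong by one visit. The documents do not support that: a subject with a first No at Week X may have followed the taper up to X, and SAP 8.2.2 carries failure forward from the next visit. What is clearly lost is a No first recorded after Week 48.
- *Other components catch these subjects.* Protocol 6.3 offers open-label rescue to those who cannot follow the taper because of flare, adrenal insufficiency or safety, and flare and rescue are read to Week 52. This stands for most taper failures. It does not cover a subject who simply stops.
- *Sites may have answered No once capsules were stopped.* That is possible. No eCRF completion instructions are in the documents, and the SAP does not require it.
- *Such subjects are visible anyway.* SAP 5.1 tabulates and lists prednisone discontinuation, SAP 8.2.2 summarises those not completing the blinded taper, and SAP 8.1.1 lists each criterion. That helps a careful reader, but the headline proportion is unchanged.

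SAP 1.1 also says that its analyses depart from the protocol because of termination. That explains the absence of tests. It does not announce a new responder definition.

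**Conclusion.** The gap is real and narrow. It affects subjects who permanently stop prednisone study drug while completing the injections, and who have Yes answers, no recorded flare and no ticked rescue. Their number is not stated and could be zero. The consequence is confined to descriptive proportions, because SAP section 8 plans summary statistics only; no p-value, error rate or power figure depends on it.

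Two stronger readings are tempting. A reader might infer that the rule favours some arms, because Arm E has active prednisone for longer. For A versus D both tapers are the same, and all arms share one blinded capsule schedule, so the opportunity to stop capsules is the same for a given starting dose. No differential bias is shown for the primary comparison, and step 5 shows that the difference could move either way. A reader might also take 2.0 or 2.9 points per subject as the size of the error, but those rest on planned denominators that the terminated study does not use.

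The conclusion assumes that permanent discontinuation of prednisone is recorded as SAP 5.1 implies, and that not following the taper in protocol 9.4.1 includes stopping it.

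**What to change.** 1. In SAP 4.6.1 and in the taper component of 8.1 and 8.2.2, add that recorded permanent discontinuation of prednisone study drug before the end of the blinded capsule schedule, or before Week X for the over-time endpoint, is a failure. Use the status field behind SAP 5.1. Do not count temporary holds, in line with the rule for the injections, and do not count stops forced by study termination.
2. Apply the rule identically in all arms on the common blinded schedule, not on each arm's last non-zero dose. A rule keyed to the last non-zero dose would fail a capsule stop at Week 30 in Arm E and pass the same blinded behaviour in Arms A to D.
3. For the Week 52 endpoint, also count a No at any scheduled or unscheduled visit after Week 48 and up to Week 52 when it refers to doses due on or before that visit.

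Before keying a rule to the schedule, the two taper tables must be reconciled. SAP Table 3 has 45 non-zero blinded weeks for the 12-month taper, matching the capsule table in SAP 7.2.2.2. Protocol Table 1 has 46, with five weeks at 4 mg against four. From a 60 mg start these end at Week 52 and Week 53 respectively.

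The cost is SAP wording and one field already collected. A few subjects may become non-responders, including some in Arms A to D who stop only zero-dose capsules; that is the price of a rule that treats the arms alike.
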